## 2.1 Primary brain tumors

Primary brain tumors are the most common primary brain tumor in the United States, and despite aggressive multimodal therapy with maximum safe resection, radiotherapy in combination with concurrent and adjuvant temozolomide, the median survival of the most aggressive form of primary brain tumor, glioblastoma, in clinical trial populations is **16 months**. There has been an unfortunate stagnation in the ability of non-invasive diagnostics to accurately differentiate between treatment response and failure. Even under optimal circumstances with the use of 'state of the art' diagnostic and therapeutic interventions, less than 15% of patients will survive five years. [8] [9] [10] While the introduction of temozolomide into the first-line standard of care [11] achieved some survival improvement, nearly all patients relapse and treatment options for recurrent disease remain limited and largely ineffective.

The ability to measure the response to treatment is a critical component in evaluating the efficacy of new therapies. Unfortunately, current diagnostic neuroimaging paradigms fail to evaluate treatment response for glioblastoma reliably. The initial landmark imaging evaluation guidelines – the Macdonald criteria – were established in 1990 and was based solely on the assessment of contrast-enhancement as a surrogate for tumor size. Contrast-enhancement is non-specific and reflects the degree of extravasation of a contrast agent across a disrupted blood-brain: changes in contrast-enhancement may be attributable to real progression, imaging technique, treatment (surgery, radiation, or chemotherapy), steroids and parenchymal changes unrelated to the tumor (postsurgical changes, ischemia, seizures). Particularly with the use of multimodal therapy with radiation and temozolomide and new systemic therapies such as bevacizumab, new radiological

phenomena including pseudoprogression and pseudoresponse have added further complexity to assessing treatment response.

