# Proprietary Information of MD Anderson

Protocol No: 2019-1032

Version No: 10

Version Date: August 25, 2023

- other pacemakers, e.g., for the carotid sinus
- insulin pumps and nerve stimulators
- non-MR safe lead wires
- prosthetic heart valves (if dehiscence is suspected)
- non-ferromagnetic stapedial implants
- pregnancy
- Claustrophobia that does not readily respond to oral medication
- Known allergy to gadolinium-based contrast agents.
- Renal failure as defined by a GFR less than 30 or the use of hemodialysis.
- Pregnant.
- Patients less than 13 years of age will be excluded.
- Interval treatment with radiation or surgery between the diagnostic MRI lesion identification and planned study MRI.
- Wards of the state

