## 7 STATISTICAL CONSIDERATIONS

### 7.1 Definitions

7.1.1 Lesion “**treatment response**” will be defined by size and contrast to noise ratio (CNR). Treatment response will be assessed only in patients with treatment prior to enrollment.

7.1.1.1 Size – treatment response in a single lesion will be considered as a decrease in size of 30%. (see section 5.1)

7.1.1.2 CNR—treatment response will be considered as a decrease in T1 post-contrast CNR of at least 20%. (see section 5.2) by standard T1 post-contrast imaging.

7.1.1.3 Lesions that do not meet these criteria for treatment response will be considered treatment failure.

7.1.2 Disease **recurrence** will be determined by surgical pathology (if available) or at least three months of imaging follow-up. Disease recurrence will be assessed only in patients with treatment prior to enrollment. Imaging findings will be considered recurrent disease in a lesion if:

7.1.2.1 The lesion was initially considered to be a treatment responder.

7.1.2.2 The lesion showed a successive increase in the size of 25% from nadir or a single imaging time point increase of 40%. (see section 5.1)

7.1.2.3 Lesions that do not meet these criteria will be considered radiation necrosis.

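### Treatment response may rest on a 20% fall in T1 post-contrast CNR with no account of steroids or bevacizumab-type therapy, which the protocol's own background says can mislead

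*Combined protocol and SAP*

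**What the plan says.** Section 7.1.1 assesses response only in patients treated before enrollment. It says that response "will be defined by size and contrast to noise ratio (CNR"), then gives two separate definitions. For size, "treatment response in a single lesion will be considered as a decrease in size of 30" per cent. For CNR, "treatment response will be considered as a decrease in T1 post-contrast CNR of at least 20" per cent, on standard T1 post-contrast imaging. It does not say whether both must be met or either is enough. There is no middle category: "Lesions that do not meet these criteria for treatment response will be considered treatment failure".

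Response status carries forward. Under 7.1.2, the first imaging condition for recurrence is: "The lesion was initially considered to be a treatment responder". Lesions that do not meet the recurrence criteria are labelled radiation necrosis (7.1.2.3). Surgical pathology is used where it exists.

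The background (section 2.1) states: "Contrast-enhancement is non-specific and reflects the degree of extravasation of a contrast agent across a disrupted blood-brain" barrier. It lists steroids among the things that can change enhancement, and says that multimodal therapy and "new systemic therapies such as bevacizumab" have brought pseudoprogression and pseudoresponse.

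The eligibility criteria (3.1, 3.2) do not mention corticosteroids or anti-angiogenic drugs. The one exclusion on treatment between scans is: "Interval treatment with radiation or surgery between the diagnostic MRI lesion identification and planned study MRI". It names no drug and ends at the study MRI, whereas response is judged on later standard-of-care scans (4.6.1).

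**The concern.** The plan describes a hazard and then adopts a rule that is exposed to it. A lesion whose enhancement falls because a steroid or a bevacizumab-type drug was started between scans can satisfy 7.1.1.2 without any change in the tumor, and no step in the plan would show that this had happened.

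Two analyses in 7.4 depend on the label. The first is the Wilcoxon rank-sum comparison of CNR between lesions that respond and lesions that do not. The second is the comparison of necrosis with progressive disease, because responder status is a precondition for calling later growth recurrent on imaging. That second comparison bears on the secondary objective (1.2.1). If some responders are drug effects, the first comparison is diluted and some labels in the second are wrong, and without exposure data in the analysis set neither could be examined.

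**Working it through.** **The plan's own figures.** The only numerical justification is the precision of mean CEST CNR in 7.3. With mean 14.9 and SD 3.0, mean ± 1.96 × SD/√n gives 14.9 ± 1.31 = 13.59 to 16.21 for n = 20, and 14.9 ± 0.88 = 14.02 to 15.78 for n = 45. Both agree with the plan. Neither concerns response, and the response comparison has no sample-size basis.

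**Is there any protection in the text?**
- Eligibility (3.1, 3.2): no condition on either drug class.
- Information listed for the imaging site (4.3): name, date of birth, contrast allergy and surgical history; no medication item.
- Follow-up (4.6.1): standard-of-care scans, with no drug information attached.
- Data handling (section 6): medical record numbers and dates are collected, so a chart could be searched, but no search is planned.
- Definitions and analysis (7.1, 7.4): no drug condition, stratification, adjustment or sensitivity analysis.

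**Does the AND/OR question settle it?** If either criterion suffices, a drug-driven CNR fall alone makes a responder. If both are required, a 30% size fall is also needed. Section 5.1.2 allows the diameter to be read on either T2 FLAIR or T1 post-contrast images, so the size criterion can itself depend on enhancement. The exposure is reduced but not removed.

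**How large could it be?** The documents give no rate of drug use, so this is an illustration.
- From the plan: 100 patients × 0.90 with tumor × 0.5 treated = 45 treated patients.
- Assumed: one lesion each, all with usable follow-up, either criterion sufficient; true response r of 30% or 50%; a share f of non-responders (10% to 50%) with a drug change; and a probability q (25% to 75%) that the change alone lowers CNR by at least 20%.
- Mislabelled share of non-responders: m = f × q, from 0.10 × 0.25 = 0.025 to 0.50 × 0.75 = 0.375.
- Spurious responders: 45 × (1 − r) × m. True responders: 45 × r.
- Share of labelled responders that are spurious: spurious / (spurious + true).

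The last column is simulated power (4,000 runs) of a two-sided 5% Wilcoxon test for an assumed true difference of 1 SD, with mislabelled lesions given the CNR distribution of the other non-responders.

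| r | m | Spurious | True | Spurious share | Power |
|---|---|---|---|---|---|
| 30% | 0 | 0 | 13.5 | 0% | 82% |
| 30% | 0.025 | 0.8 | 13.5 | 5.5% | 77% |
| 30% | 0.15 | 4.7 | 13.5 | 25.9% | 60% |
| 30% | 0.375 | 11.8 | 13.5 | 46.7% | 34% |
| 50% | 0 | 0 | 22.5 | 0% | 87% |
| 50% | 0.025 | 0.6 | 22.5 | 2.4% | 86% |
| 50% | 0.15 | 3.4 | 22.5 | 13.0% | 75% |
| 50% | 0.375 | 8.4 | 22.5 | 27.3% | 54% |

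Under the same assumption about mislabelled lesions, the expected mean difference between the labelled groups shrinks by the spurious share. That share does not depend on the number of patients. The counts and the power do, and would be lower with incomplete follow-up.

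**The case against.** Several objections have force.

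- **The CNR fall may not be sufficient alone.** The lead sentence of 7.1.1 joins size and CNR with *and*, and 7.1.1.3 speaks of criteria in the plural. A reader might infer that a drug-driven CNR fall certainly makes a lesion a responder; the text does not settle that. What stands is that it may, and that requiring both does not remove the problem.
- **The drugs may be recorded somewhere.** The appendix questionnaires and data forms are not reproduced, and charts can be searched. A reader might infer that no drug data will exist. The documents support only that no available passage plans to capture or use them.
- **The primary analysis is untouched.** A reader might infer that a primary T1-based comparison is biased. It is not: the primary objective estimates CNR by tumor type and treatment status, has no comparator and does not use the response label. T1 is the reference only in the secondary conspicuity analyses.
- **The effect on recurrence is not all harmful.** Imaging recurrence is triggered by growth, and pathology is used where available. If a truly failing tumor is wrongly called a responder and then grows, recurrence is the right label. The wrong label arises for a non-tumor lesion that shrinks and rebounds with drug changes, a subset that the documents do not allow one to size.
- **The responder comparison is peripheral.** It appears in no listed objective, has no power basis, and is done only if enough follow-up images are obtained. This limits the importance of the point but does not justify using the label unchecked.

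**Conclusion.** The point holds for the follow-up comparisons. Section 7.1.1.2 applies an enhancement-based rule without regard to exposures that section 2.1 says can change enhancement or bring pseudoresponse, and nothing in the available text restricts, captures or adjusts for them. This goes beyond missing detail, because the rule as written can produce wrong labels. Those labels enter the conditional responder test and the gate to imaging-defined recurrence.

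Its size is unknown. The illustrative range of about 2% to nearly half of labelled responders rests wholly on assumed response, drug-change and drug-effect rates, on either criterion being sufficient, and on complete follow-up. It shows that the effect could be trivial or serious; it is not an estimate. The loss of power further assumes a 1 SD true difference and that mislabelled lesions resemble other non-responders in CNR. The primary CNR estimates are unaffected. The change is worth making because it is cheap and because the confounding cannot otherwise be examined within the planned analysis.

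**What to change.** 1. For the 7T scan and each MRI used in 7.1, abstract from the chart whether corticosteroid therapy, and whether anti-angiogenic therapy, was started or changed (and in which direction) since the reference scan.
2. State in 7.1.1 whether size and CNR must both be met or either suffices.
3. Label a lesion *indeterminate* if its responder status rests on an enhancement-based fall (CNR, or size read on T1 post-contrast images) over an interval in which either therapy was started or increased. Leave it out of the 7.4 responder test. To apply this, note which sequence the diameter was read on.
4. State that indeterminate lesions do not default to radiation necrosis under 7.1.2.3, and leave them out of the imaging-based necrosis versus progression comparison unless pathology is available. Without this sentence an indeterminate lesion fails 7.1.2.1 and is labelled necrosis, which only moves the misclassification.
5. Report a sensitivity analysis that includes these lesions under the rule as it now stands in 7.1.1.

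The cost is two abstracted fields per scan, a note of the sequence, a few sentences in 7.1 and 7.4, and fewer lesions in these secondary comparisons. If both criteria are required, every responder with such a start or increase becomes indeterminate, so that loss would be larger. No change to any patient's treatment is proposed.

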## 4.6 Imaging Time Points

4.6.1 A single research imaging session will be planned for each patient. However, patients will still undergo follow-up imaging scans as part of their standard of care. These follow-up scans will serve as the basis for statistical analyses that consider treatment response or disease recurrence.

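### The three-month minimum in 7.1.2 is not tied to a scan count or a reference scan, so a growing lesion observed too little is labelled radiation necrosis by default

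*Combined protocol and SAP*

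**What the plan says.** All references are to the combined protocol and SAP.

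- **Follow-up rule (7.1.2).** Recurrence "will be determined by surgical pathology (if available) or at least three months of imaging follow-up". It is assessed only in patients treated before enrollment.
- **Imaging definition (7.1.2.1 and 7.1.2.2).** Two conditions apply: "The lesion was initially considered to be a treatment responder", and then a "successive increase in the size of 25% from nadir or a single imaging time point increase of 40" per cent.
- **Response (7.1.1).** By size, "treatment response in a single lesion will be considered as a decrease in size of 30" per cent. By CNR, "treatment response will be considered as a decrease in T1 post-contrast CNR of at least 20" per cent. Neither names the scan from which the decrease is measured.
- **Default (7.1.2.3).** "Lesions that do not meet these criteria will be considered radiation necrosis". There is no class for lesions that cannot be judged.
- **Scans (4.6.1).** "A single research imaging session will be planned for each patient". Response and recurrence are then read from standard-of-care follow-up scans, with no interval or minimum number stated.
- **Use (7.4).** Among lesions that respond and later grow, CNR is compared between necrosis and progressive disease with a Wilcoxon rank-sum test, provided there are enough follow-up images. What counts as enough is not defined. The cross-reference for follow-up images is to 4.5, which is the patient survey; follow-up imaging is in 4.6.

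**The concern.** The definition describes an ordered series of observations, but the rule for sufficient follow-up counts only months. A lesion can satisfy the time rule without having been scanned often enough for the sequence to be seen. Because 7.1.2.3 gives every lesion that misses the criteria the same label, too few scans and true absence of recurrence lead to the same result: radiation necrosis.

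The label then depends partly on how often a patient happened to be scanned. True progressors placed in the necrosis group make the two groups in 7.4 look more alike than they are. That comparison is the one in 7.4 closest to secondary objective 1.2.1, separating radiation necrosis from progressive disease. The primary CNR estimates are not affected.

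**Working it through.** The three-month figure is stated without a derivation, so there is no calculation to reproduce. The check has four parts.

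**1. Scans each route needs.** Take the 7T session as the starting point.

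- 40% route: one scan showing response (the nadir), then one showing the increase. Total 2.
- 25% route: one scan at nadir, then two consecutive increases. Total 3. The plan does not define successive. Reading it as two consecutive increases is an assumption, supported by the contrast in 7.1.2.2 with an increase at one time point.

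**2. Scans that fit in the minimum.** Take three months as 13 weeks, with the first follow-up scan one interval after the 7T session. The number of scans is floor(13 / interval). The documents give no interval, so it is varied.

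| Assumed interval (weeks) | Scans in 13 weeks | Weeks to 2 / 3 scans | Routes that can be met |
|---|---|---|---|
| 4 | 3 | 8 / 12 | both |
| 6 | 2 | 12 / 18 | 40% only |
| 8 | 1 | 16 / 24 | neither |
| 12 | 1 | 24 / 36 | neither |
| 13 | 1 | 26 / 39 | neither |

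Two scans fit only if the interval is at most 13 / 2 = 6.5 weeks, and three only if it is at most 13 / 3 = 4.3 weeks.

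If response and nadir were instead seen before enrollment, the 40% route needs 1 later scan. The 25% route needs 1 or 2, depending on whether the first increase had already been recorded. One scan fits at every interval in the table.

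**3. A lesion that is inside the 7.4 comparison and gets the default label.** Set the reference size at 100.

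- Response at a 30% decrease: 100 × 0.70 = 70, taken as the nadir.
- 25% above nadir: 70 × 1.25 = 87.5.
- 40% above nadir: 70 × 1.40 = 98 (assuming that the 40% is also measured from nadir, which the text does not say).

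Suppose that the last available scan shows a size from 87.5 to just under 98, and it is the first scan after the nadir. The lesion has responded and then grown, so 7.4 includes it. It has not reached 40%, and with one increase it cannot be successive. Under 7.1.2.3 it is called necrosis, although one more scan might have shown recurrence.

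**4. Effect on the comparison.** From 7.3, 90% of 100 patients have tumor and about half of those are treated: 100 × 0.90 × 0.5 = 45 patients. Those whose lesions respond and then grow are a subset. Let m be the fraction of necrosis-labelled lesions that are in truth progressive, with the same CNR distribution as the labelled progressors. The observed mean difference is then (1 − m) times the true one. The excess over one half of the probability underlying the rank-sum test shrinks by the same factor. For m = 0.1, 0.2 and 0.3, what remains is 90%, 80% and 70%. These values of m are illustrative; the documents give no basis for choosing one.

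**The case against.** A reader might infer that three months is simply too short for the plan's own definition. The documents do not show that. With 4-week scanning both routes fit, and with 6-week scanning the 40% route fits. Three months is also a floor: nothing caps follow-up or requires labelling at month three. Surgical pathology is a separate route that needs no serial scans. These points stand, and they make the size of the problem depend on the scan interval. They do not remove it, because nothing prevents labelling at the floor.

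A reader might also infer that a lesion with one scan at three months can never be called recurrent. That holds only if response and nadir come after the 7T session. The plan leaves this open. Section 4.6.1 and the order of events in 7.4 favour the post-session reading. But 3.1 admits treated patients whose signal is already new or increasing, so the response may lie in their earlier history. One later scan could then meet the 40% route.

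Finally, on the post-session reading, a lesion with one follow-up scan cannot both have responded and have grown, so it lies outside the 7.4 comparison even though 7.1.2.3 gives it the necrosis label. This is correct, and it is why the contamination argument rests on the responder with 25–39% growth at its last scan. The condition in 7.4 that enough images exist does not protect against that case. It is undefined, and it governs whether the analysis is run, not how a lesion is labelled.

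**Conclusion.** The concern holds in this form: the calendar minimum does not ensure that the response–nadir–increase sequence can be observed, and the default in 7.1.2.3 turns that gap into a radiation necrosis label. This is a rule that can give a wrong label when followed as written, not just missing detail.

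The frequency cannot be computed from the documents. With response judged from the 7T session, the minimum is adequate for both routes at about 4 weeks between scans, for one at about 6 weeks, and for neither at 8 weeks or more. It is less restrictive if response and nadir predate enrollment. The 25–39% example assumes that successive means two consecutive increases and that both thresholds are measured from nadir. The consequence is confined to a conditional secondary analysis in at most about 45 treated patients with tumor, where a few mislabelled lesions could matter. The change should be made.

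**What to change.** **In 7.1.2:** name the reference scan for response and for nadir, say whether scans before enrollment count, state when the three months start, and define successive.

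**In 7.1.2.3:** replace the default with wording such as:

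> Without surgical pathology, a lesion is labelled radiation necrosis on imaging only if it has at least three months of follow-up and enough evaluable scans after the nadir for either route to have been met (two, if successive means two consecutive increases), and neither was met. In the main comparison the same scan count applies to lesions labelled recurrent on imaging. Other lesions without pathology are classed as not evaluable.

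**In 7.4:** leave not-evaluable lesions out of the necrosis-versus-progression comparison, and report their number, follow-up time and scan count. As a sensitivity analysis, add lesions that met the 40% criterion with fewer scans. Correct the cross-reference from 4.5 to 4.6.

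The scan count must not depend on the outcome. If lesions meeting the 40% criterion were accepted in the main comparison with fewer scans, sparsely scanned lesions would get a label when recurrent and none otherwise, which would enrich the progressive group.

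**Cost:** mainly wording, using scans already done as standard of care and changing research labels only. Labelling comes later, and some lesions will have no label at data cut-off. Because 4.7.1 ends participation when the study scan is complete, the protocol should also make clear that later standard-of-care images may still be collected, as 4.6.1 intends.

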## 4.7 Conclusion of Study Participation:

4.7.1 Completion of planned study or volunteer scan.

4.7.2 Upon patient or volunteer request.

4.7.3 Death.

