## 7.4 Analysis Plan

Patients with metastasis are expected to have on average 2-3 detectable brain lesions each. Patients with primary brain tumors are expected to have a single lesion. All analyses will be performed on the largest lesion within patients, and some analyses will be repeated on a per-lesion basis.

The CNR for each imaging method will be determined and reported along with the corresponding 95% confidence interval. In secondary analyses, for the conspicuity endpoints, the T1 sequence by MRI will be considered the gold standard, and we will compare the conspicuity of each of the other methods to that of T1 sequencing by using McNemar's test. This analysis will first be performed in the largest lesion per patient, and then analyses will be repeated using all lesions.

If enough follow-up images are obtained (see section 4.5), we will compare the CNR in lesions that respond to treatment to those that do not by using a Wilcoxon rank-sum test. We will compare the CNR between baseline and follow-up within patient by using a Wilcoxon signed-rank test. Also, for those lesions that initially respond, some will subsequently grow in size after the initial response. Of these, some will be considered radiation necrosis and some progressive disease. The CNR will be compared between lesions with necrosis and those that are progressive disease using a Wilcoxon rank-sum test.

Exploratory aims will be analyzed with descriptive statistics. fMRI paradigms will be summarized by the group mean and standard deviation. Patient satisfaction will be reported on a five-point Likert scale and compared between the 7T scan and the most recent clinical scan by using a Wilcoxon rank-sum test.

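### Without pathology, 7.1.2 leaves patients lost before three months of imaging unlabelled or, read literally, counts them as radiation necrosis

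*Combined protocol and SAP*

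**What the plan says.** Section 7.1.2 gives two routes to a recurrence determination: it "will be determined by surgical pathology (if available) or at least three months of imaging follow-up". The pathology route has no minimum duration.

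Imaging findings count as recurrent on two conditions. The first is 7.1.2.1: "The lesion was initially considered to be a treatment responder". The second is 7.1.2.2: "The lesion showed a successive increase in the size of 25% from nadir or a single imaging time point increase of 40"%. The 40% limb can be met at one scan, and neither limb carries a time element of its own.

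The default is 7.1.2.3: "Lesions that do not meet these criteria will be considered radiation necrosis". There is no indeterminate category. The assessment covers only part of the sample: "Disease recurrence will be assessed only in patients with treatment prior to enrollment".

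Follow-up is standard-of-care imaging with no study schedule. Section 4.6.1 says of it: "These follow-up scans will serve as the basis for statistical analyses that consider treatment response or disease recurrence". Section 4.7 ends participation at "Completion of planned study or volunteer scan", on request, or at death. The labels feed one test in 7.4: "The CNR will be compared between lesions with necrosis and those that are progressive disease using a Wilcoxon rank-sum test".

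**The concern.** A waiting period has a clear purpose before a lesion is declared not to have progressed. Here it is attached to the recurrence determination itself, and the text does not say what happens when a lesion meets the growth threshold sooner or when imaging stops sooner.

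Take a lesion that responded, then grew 40% at eight weeks, in a patient who dies at ten weeks without pathology. It meets 7.1.2.1 and 7.1.2.2. If the three months run from the 7T scan, it lacks the required imaging. One analyst could call it recurrent, a second could leave it out, and a third could apply 7.1.2.3 and call it necrosis.

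Separating radiation necrosis from progressive disease is the only secondary objective (1.2). Treated patients are enrolled because their lesion is suspicious for progression (3.1), so early deterioration is foreseeable. If early loss is commoner among progressors, which is plausible but not documented, whether a patient has a correct label depends on the outcome being labelled.

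**Working it through.** **The text, clause by clause**

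- The opening sentence of 7.1.2 requires pathology or three months of imaging for a determination.
- The imaging conditions that follow (7.1.2.1 and 7.1.2.2) do not mention duration, and no sentence says that meeting them early is enough.
- 7.1.2.3 refers to failing "Lesions that do not meet these criteria will be considered radiation necrosis" without saying whether the three-month requirement is one of those criteria. If it is, early losses without pathology become necrosis. If it is not, a responder with 40% growth is recurrent at once, but a patient lost before any qualifying growth still falls to necrosis.
- The start of the three months (treatment, enrolment, 7T scan or nadir) is not given.
- Sections 4.6, 4.7 and 7.4 contain no rule for death, withdrawal or loss before three months.

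**The plan's own figures**

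The only precision figures are in 7.3, for CEST CNR with mean 14.9 and SD 3.0. Using mean ± 1.96 × SD/√n:

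- n = 20: 14.9 ± 1.96 × 3.0/√20 = 13.585 to 16.215 (stated 13.6 to 16.2).
- n = 45: 14.9 ± 1.96 × 3.0/√45 = 14.023 to 15.777 (stated 14.0 to 15.8).

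Both reproduce. No sample size, power or loss rate is given for necrosis versus progression.

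**Illustration of size**

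From 3.3 and 7.3: 100 patients × 90% tumour × about half treated = 45 treated patients.

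Assumptions, not in the documents:
- All 45 are initial responders with one lesion each.
- Half are truly progressive (22.5 against 22.5).
- There is no early loss among true necrosis.
- There is no pathology among the early losses.
- A fraction f of progressors is lost before three months.
- The true CNR difference is 3.0, which is one SD of the 7.3 example.

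Formulas:
- Lost progressors L = 22.5 × f.
- *Unlabelled reading:* progressive group = 22.5 − L. Power ≈ Φ(3.0/(3.0 × √(1/(22.5 − L) + 1/22.5)) − 1.96), a normal approximation to the rank-sum test.
- *Literal reading:* contaminated share c = L/(22.5 + L). Observed difference = 3.0 × (1 − c), taking lost and retained progressors to have the same mean CNR.

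| f | L | Progressive group if unlabelled | Power | c if counted as necrosis | Observed difference |
|---|---|---|---|---|---|
| 0 | 0 | 22.5 | 0.918 | 0 | 3.00 |
| 10% | 2.25 | 20.2 | 0.904 | 9.1% | 2.73 |
| 20% | 4.5 | 18.0 | 0.885 | 16.7% | 2.50 |
| 30% | 6.75 | 15.8 | 0.861 | 23.1% | 2.31 |
| 40% | 9.0 | 13.5 | 0.828 | 28.6% | 2.14 |

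On the unlabelled reading the cost in power is modest. Bias arises only if lost progressors differ in CNR from those retained. If they differ by one SD, the progressive-group mean shifts by 3.0 × f, that is 0.3 to 1.2.

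Sensitivity for f = 10-40%:
- Pathology in half of the early losses halves L. At f = 40% this gives c = 4.5/27 = 16.7% and a difference of 2.50.
- With a true progressive share of 30%, c is 4-15% and the difference 2.88-2.56.
- With a share of 70%, c is 19-48% and the difference 2.43-1.55.

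**The case against.** The strongest reply is that a minimum observation period before either call is defensible. The Background (2 and 2.1) describes pseudoprogression and radiation necrosis as hard to separate from recurrence, and 7.4 expects some lesions that grow after response to be necrosis. This stands. A reader might infer that waiting is pointless once growth reaches the threshold. The documents do not support that, so an early growth call should be flagged and tested.

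Three other strong readings also fail:

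- *Early progressors can have no valid progressive label.* Surgical pathology gives one with no time minimum. The gap concerns lesions without pathology.
- *The progressive group is certainly and selectively depleted.* The literal default is necrosis, so misclassification is at least as likely as depletion. If the three months run from treatment, many patients may already satisfy them at enrolment.
- *The number affected follows from the 16-month median survival in 2.1.* That figure is for glioblastoma, described there as the most aggressive primary tumour. An early death costs a label under this rule only if pathology is absent, and it costs a progressive label only if the lesion had also responded and been imaged growing.

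It can also be said that 7.4 appears to restrict the comparison to lesions that responded and then grew. If that restriction is enforced, patients lost before any growth do not enter, and contamination would be smaller than in the table. Section 7.1.2.3 does not contain the restriction.

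Finally, the primary CNR estimates come from the single 7T session and are untouched, and the follow-up comparisons open with a condition that enough follow-up images exist. Both points limit the importance of the gap without closing it. The bar on non-responders in 7.1.2.1 is a separate matter.

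**Conclusion.** The concern holds for lesions without surgical pathology. As written, 7.1.2 permits conflicting labels for a lesion with qualifying growth before three months. Under 7.1.2.3, patients with too little follow-up are counted as necrosis without evidence of it. No other section repairs this.

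The size cannot be established from the documents. The illustrative range of 9-29% contamination, with a difference of 3.0 falling to about 2.7-2.1, rests on the assumed equal split, no pathology, universal initial response, loss confined to progressors, and equal CNR in lost and retained progressors. Pathology or a smaller progressive share reduces it; a larger progressive share increases it. Selective loss of progressors is a plausible inference and is not shown by the documents. The affected analysis is the necrosis-versus-progression test serving the secondary objective. The plan should be changed before these labels are assigned.

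**What to change.** In 7.1.2 and 7.1.2.3:

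1. Define the start of the three months.
2. Allow a necrosis label only with pathology, or with at least three months of imaging without qualifying growth.
3. Label lesions that have neither pathology, qualifying growth nor three months of imaging as not classifiable, never as necrosis.
4. State that a lesion meeting 7.1.2.1 and 7.1.2.2 before three months is never defaulted to necrosis. Count it as progressive and flag it as an early call.

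In 7.4:

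5. Report the number of not-classifiable lesions and their baseline 7T CNR, by reason (death, withdrawal, imaging stopped).
6. Repeat the necrosis-versus-progression comparison without the flagged early calls.

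The cost is a few sentences and one sensitivity analysis. It changes outcome labels only and adds no scan. The reason for loss has to be recorded, but attribution of cause of death, which the plan does not describe collecting, is not needed. The downside is that some early growth may be transient treatment effect; the flag and the sensitivity analysis show how far the result depends on it.
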